### **7.2.2. Intention-to-Treat Population:**

The intention-to-treat population, defined above in section 5.1 (Full Analysis Population), will serve as the population for all primary analyses.

All participants must have successfully completed the baseline assessment, been randomized, and received at least their first supply of cigarettes. This means that the intention-to-treat population must have, at a minimum, completed the second baseline session.

### **7.2.3. Safety Population**

The population for all safety analyses includes all participants who received any study cigarettes, excluding participants who dropped out prior to randomization. Note that participants are randomized at the end of the first baseline visit, but the VLNC condition does not receive research cigarettes until the second baseline visit, so this population effectively includes all participants attending at least the second baseline session.

## **7.3. Primary Endpoint Analysis**

### **7.3.1. Primary Analysis**

The primary endpoint is CPD during Week 12, compared to the CPD at baseline. While the primary outcome is the mean total CPD, consisting of both study and non-study cigarettes, the analyses will be repeated examining only the CPD contributed by study cigarettes. CPD will be computed as the mean CPD calculated on a weekly basis. Data analysis will use repeated measures analysis of variance, with two conditions and two time points (baseline and Week 12). In addition, the analysis model will include a random effect for site, a random

participant effect and random error (within-subject error). Variance parameters will be estimated using restricted maximum likelihood method with the Satterthwaite approximation.

Because CPD will be measured weekly, additional analyses will be performed including data collected at all time points. The analysis will be conducted in a manner similar to that described above, with the exception that there will be 13 time points: baseline and Weeks 1 through 12. For these analyses, the variance-covariance structure will be specified as first-order autoregressive.

Additional outcomes include the CPT, breath CO level, urinary cotinine concentration, and nicotine dependence and withdrawal scores. These will be examined in a manner similar to that described above for CPD. Natural log transformations will be performed as needed so that ANOVA model assumptions of normality and equal variances hold. Geometric means in original units will be calculated as well. Note that not all outcomes are assessed at weekly in-person visits. The time points at which each outcome is assessed is described in Section 6.

Finally, several assessments will be made at baseline as well as at the abstinence visit, which occurs the day following the Week 12 assessment. At this visit, measures of craving and withdrawal will be completed. The analysis will be similar to that described above for the CPD comparing baseline CPD to that reported at the end of the trial. The analysis will deviate from that described only in the timing of the tasks, with the time points consisting of the baseline and the abstinence visits, rather than the baseline and Week 12 visits reported above.

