Participants will be required to keep track of all the cigarettes provided to them. Therefore, they will be instructed to return all unused cigarettes and empty cigarette packs to the laboratory each week. Research staff will complete the 'Product Accountability Log' as they process participants' products. Any discrepancies in the product dispensed versus product returned will be discussed and recorded in the log. Empty cigarette packs will not be saved; however, research staff will keep all empty cartons in storage for reference. Unused cigarettes will be re-distributed to the participants during Weeks 1-12. Any remaining unused cigarettes returned by the participants will be collected by the research staff.

If participants lose more than two packs of cigarettes and require an unscheduled visit to the laboratory to supplement their supply, they will be told the next time they lose more than two packs they will have to wait until their next scheduled appointment to receive more cigarettes.

Study 2 Statistical Methods and Sample Size

Continuous outcomes will be summarized by the mean, standard deviation, median and range. Categorical outcomes will be summarized by frequencies and percentages. Skewed continuous outcomes will be log- or square-root transformed as appropriate. Variables measured at each baseline visit will be averaged and the average will be used as the baseline measurement. As we expect conditions will be balanced on important baseline characteristics due to randomization, our primary analysis for all endpoints will not be adjusted for potential confounders. However, a secondary analysis will be completed for all outcomes adjusting for demographic characteristics (e.g., age) that we found to be important in prior studies. Potential moderators such as obesity (BMI above or below 30) will be explored by adding that term to the model and the moderator-by-condition term to the model.

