The Primary Aim of Study 2 is to compare the effects of cigarettes varying in nicotine yield on smoking rate. The primary endpoint is cigarettes per day (CPD) at 12 weeks. CPD will be collected by daily IVR and/or TLFB at each session to assess cigarette use in the days since the last interview. This will yield a continuous record of cigarette use throughout the study. A weekly average will be obtained for analysis by averaging CPD from the previous visit to the current visit. Additional measures addressing this aim are breath CO level, urinary cotinine concentration, and nicotine dependence (FTND, WISDM) scores. Secondary Aim 1 is to assess adherence to assigned tobacco products and use of multiple nicotine

products during extended exposure. Secondary Aim 2 is to quantify the effects of VLNC cigarettes on (a) biomarkers of exposure to tobacco carcinogens (urine total cotinine, NNAL, PAH)s.

To examine these Aims, repeated measures analysis of variance (ANOVA) will be used for outcomes that are measured repeatedly from baseline to the end of the treatment phase. Each repeated measures ANOVA model consists of five terms: cigarette condition effect, visit effect, interaction effect between cigarette condition and visit, random subject effect (between-subject error), and random error (within-subject error). The variance-covariance structure will be specified as the first-order autoregressive, and variance parameters will be estimated using restricted maximum likelihood method with the Satterthwaite approximation. First, the VLNC condition will be compared to the usual brand condition; if significant differences are observed ($p < 0.05$), the simple effects of visit will be examined within the VLNC condition and the usual brand condition. Biomarkers will be analyzed on natural log scales so that ANOVA model assumptions of normality and equal variances hold. Geometric means in original units will be calculated as well. Interaction terms between BMI and cigarette condition will be added to these models to explore possible moderating effects of obesity on the relationship between cigarette condition and biomarkers. Differences between groups in self-reported quit and cigarette reduction rates at the 4-week post-treatment follow-up period will be evaluated using Chi-square tests, as will be the case for other discrete outcomes such as drop-out rates. SAS (SAS Institute Inc., USA) will be used for most analyses, but may be supplemented by use of STATA or R.

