## **7.6. Missing Data**

We will test the pattern of missing values using Little's MCAR test, and, assuming that the data are missing at random, we will employ statistical procedures that are based on maximum likelihood estimates, which will allow the inclusion of all subjects without imputation of missing values. The maximum likelihood approach estimates the parameter values that would maximize the probability of observing the data collected. In the event of missing variables, the likelihood for a given individual is the probability of observing the non-missing variables. Thus, the maximum likelihood approach allows the use of data from participants for the time period for which data is available, but not for time periods for which the data is missing. This procedure uses information from earlier time periods to estimate the effects of later time periods, while also accounting for the uncertainty of the projection in the computation of standard errors and test statistics. While maximum likelihood estimation is considered superior to imputation methods for the treatment of missing data in clinical trials, additional analyses will be conducted using several imputation methods to test the sensitivity of these results. Imputations methods will include, but not be limited to, last observation carried forward and multiple imputation with the Markov Chain Monte Carlo (MCMC) method carried out in PROC MI in SAS.

In the case of non-random missing data, we will conduct sensitivity analyses using

multiple imputation with the Markov Chain Monte Carlo (MCMC) method carried out in PROC MI in SAS. If missing data is associated with experimental condition, we will conduct multiple imputation for each experimental condition. At least 10 imputed data sets will be generated, with the experimental-condition effect being assessed in each imputed data set. A final single assessment of experimental condition differences will be obtained from combining the results across the imputed datasets using PROC MIANALYZE in SAS. The results of these analyses will be compared to the primary analysis to evaluate the robustness of our conclusions.

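### The primary Week 12 CPD test uses baseline CPD as a response; adjusting for it as a covariate would be at least as precise, for one degree of freedom

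*SAP*

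**What the plan says.** SAP 7.3.1 defines the endpoint as a comparison with baseline: "The primary endpoint is CPD during Week 12, compared to the CPD at baseline". The model is given as "Data analysis will use repeated measures analysis of variance, with two conditions and two time points (baseline and Week 12", and "the analysis model will include a random effect for site", together with a random participant effect and residual error, fitted by REML with Satterthwaite degrees of freedom. The weekly values come in only afterwards, where "additional analyses will be performed including data collected at all time points" under a first-order autoregressive (AR(1)) structure with 13 time points.

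SAP 7.1 lets either a condition effect or a condition-by-visit interaction lead to post-hoc tests. SAP 4.2 sizes the trial on a between-condition difference in CPD at the end of the trial: 45 completers per condition, 80% power, alpha 0.05. SAP 7.6 describes the likelihood approach to missing data: "This procedure uses information from earlier time periods to estimate the effects of later time periods".

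The protocol (Study 2 Statistical Methods and Sample Size) gives one generic model for outcomes measured repeatedly from baseline to the end of treatment: "Each repeated measures ANOVA model consists of five terms: cigarette condition effect, visit effect, interaction effect between cigarette condition and visit", plus random subject and residual error. It also says: "The variance-covariance structure will be specified as the first-order autoregressive". It names no site term, and it says that "our primary analysis for all endpoints will not be adjusted for potential confounders". SAP 13 declares no change from the protocol's analyses.

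**The concern.** When baseline is a response level in a two-point model, the interaction is the difference between arms in mean change. A change score in effect fixes the slope of Week 12 on baseline at 1. A covariate adjustment estimates that slope. Unless the true slope is 1, the change score carries avoidable variance.

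The two-point model also uses no CPD from Weeks 1 to 11. For a woman who leaves before Week 12, only her baseline can inform the missing value, although SAP 7.6 relies on earlier periods to inform later ones.

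At stake is power on the primary endpoint, and clarity about which number decides the trial. Validity is not in question.

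**Working it through.** **Inputs.** From SAP 4.2: 45 completers per arm, 80% power, alpha 0.05, and a 5 CPD difference suggested by preliminary data. From the protocol (Study 2 Randomization): 1:1 allocation and a goal of 106 randomised. Not given anywhere: the SD of CPD, the baseline-to-Week 12 correlation (rho), and sidedness for Study 2. I assume a two-sided test and vary the rest.

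**The plan's own figures.** Enrolment reproduces: 90/0.85 = 105.9, rounded up to 106, plus 5 pilots = 111. The 45 per arm cannot be reproduced without an SD. Solved backwards (noncentral t, 88 df), 80% power needs a standardised difference of 0.597, so the SD is 5/0.597 = 8.37.

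**Direction.** Let s0 and s12 be the baseline and Week 12 SDs. Per participant:
- change: s0² + s12² − 2·rho·s0·s12
- adjusted Week 12: s12²(1 − rho²)
- difference: (s0 − rho·s12)², which is never negative.

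No assumed value is needed for this.

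**Size, as sample size.** Let k = s12/s0. The ratio of variances is (1/k² + 1 − 2·rho/k)/(1 − rho²), which is 2/(1 + rho) at k = 1. Per-arm number for the change test to match 45 per arm adjusted:

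| k (assumed) | rho 0.3 | rho 0.5 | rho 0.7 |
|---|---|---|---|
| 1 | 45 × 1.54 = 69 | 45 × 1.33 = 60 | 45 × 1.18 = 53 |
| 0.8 | 45 × 1.99 = 90 | 45 × 1.75 = 79 | 45 × 1.59 = 72 |
| 1.25 | 45 × 1.27 = 57 | 45 × 1.12 = 50 | 45 × 1.02 = 46 |

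**Size, as power.** This is for 5 CPD, 45 per arm and equal SDs. Change uses SD·√(2(1 − rho)) with 88 df; adjusted uses SD·√(1 − rho²) with 87 df.

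| The stated 80% refers to | Test | rho 0.3 | rho 0.5 | rho 0.7 |
|---|---|---|---|---|
| A: end-point CPD (SD 8.37) | change | 65.8% | 80.0% | 95.1% |
| | adjusted | 83.6% | 89.9% | 97.5% |
| B: change (SD of change 8.37) | change | 80% | 80% | 80% |
| | adjusted | 93.5% | 89.9% | 86.0% |

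Under B the implied end-point SDs are 7.08, 8.37 and 10.81. A simulation of A (20,000 runs per rho) gave change 66.4 / 80.3 / 95.3% and adjusted 83.4 / 89.4 / 97.6%. Null rejection was 5.0 to 5.3% for change and 4.8 to 5.2% for adjusted.

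**Cost.** One degree of freedom. With 90 completers the estimated slope multiplies the variance by 1 + 1/(90 − 4) = 1.012, so the SE by 1.006. If rho were 0 under A, the adjusted test would have 79.5% power against 80.0% for an unadjusted Week 12 contrast; the change test would have 50.8%.

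**Weeks 1 to 11.** With 53 randomised per arm, 15% leaving evenly over time and an assumed known covariance, using the weekly data lowers the variance of the adjusted contrast by a further 3 to 6%.

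**Choice of covariance.** This matters if the weekly data are used. Suppose correlation follows AR(1) at 0.90 per week. After adjustment for baseline, residual variance is 1 − 0.90² = 0.19 at Week 1 and 1 − 0.90²⁴ = 0.92 at Week 12. A constant-variance AR(1) model with baseline-by-visit fits one common value, about 0.64. The Week 12 SE is then too small by √(0.64/0.92) = 0.83, and large-sample null rejection is 10.3%. At 0.95 per week the values are 0.10, 0.71 and 0.43, with rejection 12.5%. With a random participant effect of 0.4 plus AR(1) 0.8 it is 8.8%. Simulation at 45 per arm (600 runs) gave 10.2% and 10.3% for the two AR(1) cases, against 5.5% and 3.8% for Week 12 ANCOVA on the same data. Under exchangeable correlation the rate stays at 5.0%.

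**Protocol against SAP.** At two time points, AR(1) and a random participant effect give the same covariance if the correlation is non-negative, so the AR(1) wording does not change the two-point test. Two differences remain. The SAP adds a random site effect (SAP 7.1 still says five terms but lists six). The SAP also makes the two-point model primary and the all-visit model additional, where the protocol describes only the all-visit model.

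**The case against.** - **Both tests are valid.** This is true. A reader might infer that the planned test is biased or has the wrong size; it is unbiased and holds 5%.
- **The deciding term is clear enough.** Largely so: comparing Week 12 with baseline points to the interaction. Naming it still matters. Under A at rho 0.5 a condition main effect over the two time points would have 37% power against 80%, because it averages in a baseline where no difference is expected.
- **Two terms, each tested at 0.05.** A reader might infer a type I error near 1 − 0.95² = 9.75%. The documents do not support that: SAP 7.1 uses the either-or only to trigger post-hoc tests.
- **Weekly data and missing data are already covered.** In part. The 13-point analysis and the imputation analyses exist, but as additional or sensitivity work; the primary test does not use Weeks 1 to 11.
- **Adjustment can lose participants.** This stands. The SAP's intention-to-treat population (5.1, 7.2.2) needs only Baseline 2 and receipt of cigarettes, and 7.6 promises inclusion of all subjects. A woman with no later CPD stays in the present likelihood but drops out if baseline is only a covariate.
- **The protocol excludes adjustment.** It excludes adjustment for confounders, on the ground of expected balance. Baseline CPD would be used for precision, and the plan should say so.

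**Conclusion.** The point holds as a low-cost improvement in efficiency and clarity. In large samples the adjusted Week 12 contrast is never less precise than the planned change test, whatever the SDs and rho. The size cannot be fixed from the documents. Under A, over rho 0.1 to 0.9 at equal SDs, the interaction runs from 55% to above 99% and the adjusted test from 80% to above 99%. Under B the adjusted test runs from 96.5% down to 82.0% against 80%. At equal SDs the gain is small when rho is high: about 2 points at 0.7 under A and at 0.9 under B.

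A reader might infer that the trial is underpowered. That would need the SD and rho, which are not given. A reader might also infer that the two documents specify incompatible covariance models for the primary test. At two time points they do not; the unreconciled parts are the site term and which analysis is primary, set against SAP 13.

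**What to change.** 1. In SAP 7.3.1 name one primary test: the between-arm difference in mean total CPD at Week 12, two-sided 0.05, adjusted for baseline CPD, keeping the site effect, reported with a 95% confidence interval.
2. Obtain it by ANCOVA at Week 12 or, to keep all intention-to-treat participants and use Weeks 1 to 11, by a mixed model over baseline and Weeks 1 to 12 with a common baseline mean and an unstructured (or heterogeneous-variance) covariance. Do not use constant-variance AR(1) with baseline-by-visit, for the reason shown above.
3. Keep the two-point change analysis as supportive.
4. State that adjustment for baseline CPD is not the confounder adjustment that the protocol leaves out of the primary analysis.
5. Reconcile the protocol's Study 2 statistical section with SAP 7.1 and 7.3.1 on the site term and on which analysis is primary, and list the change in SAP 13.
6. Confirm that participants do not know their condition during the baseline week. SAP 5.1 starts randomisation after Baseline 1, while the protocol randomises at the end of Baseline 2 and collects baseline CPD between the two visits. This bears equally on the change analysis.

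The cost is wording and one degree of freedom. Baseline and weekly CPD are already collected.

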Participants will receive a follow-up phone call between 25 and 35 days after the abstinence assessment session to assess their smoking patterns. The phone questionnaire will last less than five minutes. The questionnaire will ask if the participant is still smoking, how much and whether she has attempted to quit smoking since the end of the study. Participants will receive 5 variable incentive program lottery tickets for completing the call as compensation. Those who report abstinence will be invited to complete for biochemical verification and be compensated \$40 for doing so. A urine sample will be collected to test urine cotinine levels. Additionally, any Medical Event Forms that remain open from the last session will be discussed.

Once a participant has completed all study procedures and all open events have been closed, the PI or project manager will review the participant's records and sign a form indicating study completion for that participant.

Birth Outcomes Data

Researchers will collect birth outcome data through review of maternal birth medical records.

Study 2 Randomization

At the end of the Baseline 2 session, participants will be randomized into one of two cigarette conditions. Participants in each condition will be assigned cigarettes that match their menthol preference. Participants will be randomized, using block randomization, in equal number to the dose conditions, with randomization stratified by study site and menthol status. Each site will randomize participants until the total goal of 106 participants across both sites is reached, and no effort will be made to recruit a specific number of menthol and non-menthol smokers at each site.

Condition	TPMF Code	Type*	Specifications Nicotine Yield	Specifications Tar Yield	Specification Range for Nicotine Yield	Specifications Nicotine Content
2	NRC102	RN	0.03 ± 0.01	9 ± 1.5	0.02 - 0.04	0.37 ± 0.01
2	NRC103	RN-Men	0.03 ± 0.01	9 ± 1.5	0.02 - 0.04	0.39 ± 0.00
3	N/A	Usual Brand	N/A	N/A	N/A	N/A
3	N/A	Usual Brand-Men	N/A	N/A	N/A	N/A

*Legend:	
RN	Reduced Nicotine
RN-Men	Reduced Nicotine-Menthol

The lead statistician will create a randomization schedule for each of the two sites, amounting to 150% of expected enrollment at each site. The excess randomization codes will be used in the event that a site will have to enroll extra participants due to unexpectedly slow enrollment at another site.

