#### 4.1. Condition Assignment/Randomization

The study consists of two baseline assessments, separated by one to three weeks, 12 weeks of extended exposure to research or usual brand cigarettes, with assessments completed weekly, an abstinence assessment the day following the Week 12 visit and a final assessment 30 days after completing the study.

Participants will be randomly assigned to one of the two conditions, with randomization stratified by site and menthol preference. The lead statistician will create a randomization schedule for each site, amounting to at least 150% of expected enrollment at that site. The excess randomization codes will be used in the event that a site will have to enroll extra participants due to unexpectedly slow enrollment at another site.

The assumptions needed to generate the randomization schedule for this study are summarized in Table 2. The final randomization sequences were generated January 18, 2022. There are two major types of assumptions: 1) the proportion of participants recruited from each site, and 2) the proportion of recruited participants at each site who smoke menthol/non-menthol cigarettes. The recruitment goal for this study is 111 people. A sample size of 90 completers is proposed to test the primary aim in Study 2. Anticipating 15% attrition, and five pilot participants (3 at UVM, 2 at the University of Kentucky [UK]), 111 participants will be enrolled across both sites (74 at UVM, 37 at UK).

Participants will be recruited from the University of Vermont (UVM) and the University of Kentucky (UK). In the acute exposure portion of this project, 19% of the smokers at UVM used menthol and 81% smoked non-menthol cigarettes. Based on data from previous studies conducted at UK, menthol was assumed to be the preferred flavor for 33% of the UK participants. For ease of calculations, the UVM estimate was rounded to 20% menthol smokers.

The assumption for the extended exposure study is that 67% of the smokers recruited will come from UVM, with the remaining 33% from UK. From this it follows that 74 participants will be recruited at UVM ( $=0.67*111$ ) and 37 at UK ( $=0.33*111$ ).

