## **7. Statistical Analysis**

### **7.1. General Approach**

To examine these Aims, repeated measures analysis of variance (ANOVA) will be used for outcomes that are measured on multiple occasions from baseline to the end of the intervention phase. Each repeated measures ANOVA model consists of five terms: cigarette condition, visit, interaction between cigarette condition and visit, a random effect for study site, a random participant effect (between-subject error), as well as random error (within-subject error). Variance parameters will be estimated using restricted maximum likelihood method with the Satterthwaite approximation. In the event of a statistically significant condition effect or a condition-by-visit interaction, post-hoc tests will be conducted in order to explore the nature of the significant findings.

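### Site has only two levels but is fitted as a random effect: the treatment contrast is essentially unaffected, but site adjustment can drop out and any interval shown for a condition mean can be far too wide.

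*SAP*

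**What the plan says.** SAP 7.1 (General Approach) sets out the repeated-measures model for all outcomes measured on several occasions. Besides condition, visit and their interaction, it includes "a random effect for study site". SAP 7.3.1 repeats this for the primary comparison of baseline with Week 12 CPD: "In addition, the analysis model will include a random effect for site". Both sections specify REML with the Satterthwaite approximation. SAP 7.3.1 carries the approach over to breath CO, cotinine, the purchase task, dependence and withdrawal, and SAP 7.4 to most secondary endpoints.

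SAP 4.1 names two recruiting sites, Vermont and Kentucky, with 74 and 37 participants planned. Assignment is made "with randomization stratified by site and menthol preference". The Protocol (Study 2 Randomization) adds that participants are block-randomized "in equal number to the dose conditions, with randomization stratified by study site and menthol status".

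Neither document says what happens if the site variance is estimated as zero. The model in the Protocol (Study 2 Statistical Methods and Sample Size) has no site term, so it gives no reason for treating site as random.

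On output, SAP 7.3.1 and 7.4 call for geometric means, and SAP 11 covers means, standard deviations, quantiles, p-values and coefficients. No section commits to confidence intervals for condition means.

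**The concern.** A random effect treats the sites as a sample from a population of sites and estimates the variance of that population. Two sites give 2 - 1 = 1 degree of freedom for it, and REML then does one of two things.

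- If the two site means differ by no more than sampling noise would produce, the variance is set to zero and site leaves the model. The factor on which randomization was stratified is then not adjusted for. This is decided separately for each outcome, so CPD could be site-adjusted while cotinine in the same report is not.
- If the estimate is positive, its uncertainty enters the standard error of each condition mean. Satterthwaite degrees of freedom fall close to 1, where the 95% t multiplier is 12.7 (4.30 at 2 df), against 1.99 at about 87 df.

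What is at stake is consistent adjustment for a design factor and the readability of any error bars on condition means. The test of the cigarette condition is not at stake.

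**Working it through.** **Inputs from the documents.** Two sites, 74 and 37 enrolled; 90 completers, 45 per condition; 80% power; a 5 CPD difference; alpha 0.05; mean 12.1 CPD (SAP 4.1 and 4.2).

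**The plan's own figures.** SAP 4.1 builds the enrolment figure thus: "Anticipating 15% attrition, and five pilot participants". 90/0.85 = 105.9, rounded up to 106; 106 + 5 = 111, which reproduces the plan. The 80% power cannot be reproduced independently because no SD is given. Solving for it (two-sided test assumed), SD = 5 / [(1.960 + 0.842) × √(2/45)] = 8.47 CPD; the t-based version gives 8.37. I use 8.4 by hand and 8.46 in the simulation.

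**Assumptions not in the documents.** That SD; equal attrition by site, giving 90 × 74/111 = 60 and 90 × 37/111 = 30 completers; a between-site SD of 0 to 4 CPD; a baseline to Week 12 correlation of 0.5; complete data.

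**Step 1: chance that the site variance is zero.** With effective site size n0 = 90 - (60² + 30²)/90 = 40, the probability is P[F(1, 87) < 1/(1 + 40·s²/SD²)], where s is the between-site SD. For s = 2 the bound is 1/(1 + 40 × 4/70.56) = 0.306, giving 42%. For s = 0, 1, 2, 3 the results are 68%, 57%, 42% and 31%. The 68% at s = 0 does not depend on the SD. This formula uses one measurement per participant; step 3 uses the planned two-time-point model.

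**Step 2: one case by hand.** Suppose the observed site means differ by d = 3 CPD.

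- Noise: 70.56 × (1/60 + 1/30)/2 = 1.764. The estimate is zero whenever d²/2 < 1.764, that is, |d| below about 1.88 CPD.
- Site variance: 9/2 - 1.764 = 2.736.
- Residual part of a condition mean, 30 and 15 per site, sites weighted equally: 70.56 × (1/30 + 1/15)/4 = 1.764.
- Variance of the condition mean: 2.736/2 + 1.764 = 3.132; SE 1.77.
- Satterthwaite df: 2 × 3.132² / [2 × (9/4)²] = 1.94; t = 4.44.
- 95% half-width: 4.44 × 1.77 = 7.9 CPD.
- With site fixed: 1.99 × √1.764 = 2.6 CPD.

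**Step 3: the planned model.** REML for two conditions and two time points with participant and site effects, 60/30 completers, 2,000 simulated trials per setting. The last three columns refer to runs with a positive site variance.

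| Between-site SD (CPD) | Variance zero | Median half-width, Week 12 condition mean | Median df | Half-width above 12.1 CPD |
|---|---|---|---|---|
| 0 | 68% | 5.0 | 2.8 | 7% |
| 1 | 55% | 6.1 | 2.3 | 15% |
| 2 | 39% | 9.1 | 1.8 | 38% |
| 3 | 29% | 13.3 | 1.5 | 54% |
| 4 | 22% | 19.9 | 1.3 | 65% |

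When the variance is zero, the half-width is about 2.5 CPD. With site fixed it is about 2.5 (sites weighted by size) or 2.7 (equal weights), whatever the site difference.

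**Step 4: the treatment contrast.** A site intercept is the same at baseline and Week 12, so it cancels from each participant's change. Power for condition-by-visit was 79-81% in every 60/30 setting. The SE of the between-condition difference in participant means was 1.52 to 1.55 CPD whether or not the site variance was zero, because allocation is balanced within site.

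**The case against.** The strongest reply is that no planned test changes. The primary comparison is change in CPD by condition, the site intercept cancels from it, and 1:1 blocked allocation within site makes site nearly orthogonal to condition. That stands. A reader might infer that one degree of freedom for site weakens or invalidates the primary test. The documents do not support this: the SAP specifies only a site intercept, with no random site-by-condition term, and step 4 shows power and SE unmoved. With missing visits the cancellation is near rather than exact.

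Second, a reader might infer that the SAP plans to publish the wide intervals. It does not say so. It asks for geometric means and lists means and SDs; standard errors are mentioned only in the missing-data section (SAP 7.6). The harm is therefore conditional on a standard error or interval from the model being shown beside a condition mean. That is a natural output of such a model, but not a stated one.

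Third, a zero estimate costs almost nothing in precision: about 2.5 CPD against 2.5 to 2.7 with site fixed. That also stands. What remains is that adjustment for a stratification factor depends on the data of each outcome.

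Fourth, random site targets sites in general and fixed site targets these two. The distinction is legitimate, but two sites cannot support the wider inference, as the 1 to 3 degrees of freedom show.

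**Conclusion.** The concern holds as a minor modelling point. With two sites, the random site term does not reliably do what it was put there for. For between-site SDs of 0 to 3 CPD, it drops out in roughly 30-68% of trials. Otherwise it leaves condition means with about 1.3 to 3 degrees of freedom and median half-widths about 2 to 5 times those with site fixed (5.0/2.5 = 2; 13.3/2.5 = 5.3), and wider still in many runs. Even when the sites do not truly differ, a positive estimate doubles the interval; from a between-site SD of about 2 CPD, intervals become hard to interpret against a mean of 12.1 CPD.

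The sizes rest on a back-solved SD, an assumed 60/30 split, an assumed correlation and assumed site SDs. The single degree of freedom does not. The result should not be read as a threat to the primary conclusion or to any between-condition comparison.

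**What to change.** In SAP 7.1 and 7.3.1, replace the random effect for (study) site by a fixed effect for site. The wording in 7.1 then carries through to the additional and secondary outcomes. If model-based condition means are to be shown, add a phrase saying whether sites are weighted equally or by size, since this moves the half-width between about 2.7 and 2.5 CPD.

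The cost is one degree of freedom out of about 88, with power unchanged at about 79-81% for 90 completers, and inference formally limited to these two sites. No new data and no change to conduct are needed.
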